## 2.4.3. CLN-PRO-V002 Study Results (24 M)

Recruitment began in October 2013 and was completed in June 2014 with 20 patients implanted. Thirteen patients completed the 2 year follow up visit. Of the seven patients terminating the study early, three died and four were withdrawn after occlusion of the HAV. None of the deaths were considered related to the investigational device or procedure.

Kaplan-Meier analyses in which deaths were censored revealed primary, primary assisted, and secondary patency probability rates of 79.2%, 79.0%, and 89.5% at Week 26, 63.3%, 63.2%, and 84.2% at Month 12, 63.3%, 63.2%, and 79.0% at Month 18, and 58.1%, 57.9%, and 73.7% at Month 24.

Six patients (30%) required at least 1 graft intervention to maintain or restore HAV patency during the study. Four patients required 1 intervention and 1 patient each required 3 and 4 interventions. Most interventions successfully restored patency. However, in 1 patient the graft patency could not be restored and the HAV was replaced with an alternative bypass graft. Two patients, who had previously undergone successful interventions, developed a recurrent thrombosis which was not treated and the HAV was left occluded. Two patients experienced HAV thrombosis with no or minimal symptoms and refused interventions on the HAV.

Confidential

All 20 patients experienced AEs (a total of 92 events). Thirty-one of these events in 13 patients were considered serious. The most frequent AEs reported included graft thrombosis (35% of patients), anastomotic stenosis (20% of patients), lymphocele (20% of patients), and local swelling (15% of patient). Those serious adverse events (SAEs) reported by at least 2 patients were graft thrombosis (6 patients, 30%) and anastomotic stenosis (2 patients, 10%).

No patient showed an increase in PRA levels. Two patients had a significant (>2-fold) increase from baseline in IgG levels. One of these patients experienced a thrombosis of the HAV between 3 and 6 months after implantation, while the other patient has had no HAV-related AEs and continues to have primary patency. Neither patient has had any evidence of dilatation or structural degeneration of the HAV.

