The assignment to a patency (yes/no) (primary, primary assisted, secondary patency) will be verified during the Data Review Meeting (DRM) using all data of CRF sections referring to HAV patency, clinical examination of the HAV site, doppler ultrasound assessment of HAV patency, HAV intervention, premature discontinuation, and AEs.

Patency rates will be presented with frequency tabulations showing patient numbers and patency rates for Month 12.

Clopper-Pearson confidence intervals (CI) will be presented for frequency counts of patency rates.

Kaplan-Meier (K-M) curves for primary, primary assisted, and secondary patency will be created at the 1-year report and for all subsequent reports. K-M curves will be provided using two censoring methods:

- a. Patients who die, withdraw from the study, or are lost to follow-up are censored at the day of the respective event.
- b. Patients who die, withdraw from the study, or are lost to follow-up are considered as having suffered failure of secondary patency at the day of the respective event.

Efficacy Objective #2:

Hemodynamically significant stenosis (>70% by duplex ultrasound criteria): The duplex ultrasound parameters will be summarized by planned visit up to Month 12.

- Frequency of stenosis occurrence, location of stenosis, and presence of aneurysm.
- Numeric summary of volumetric flow rate and inner diameter of HAV mid bypass.

A stenosis event can occur between planned study visits (i.e. Unscheduled Visits). A "by visit"

Statistical Analysis Plan	
CLN-PRO-004	

summary will represent the stenosis event/information that occurred before or on the planned visit. For example, the summary at Day 5 will denote the number of patients who had stenosis occur up to Day 5 or on the Day 5 visit. Similarly, the Day 29 summary will denote the number of patients with stenosis events that occurred after Day 5, and up to Day 29 (inclusive of Day 29).

The time of first stenosis (in days) will be summarized and calculated as number of days from HAV implantation to date of first stenosis event: Date of Stenosis – Date of Day 1 + 1. Patients who did not have a stenosis event will not contribute a value for this summary.

Please note, the clinical duplex will be recorded for all visits. Results after Month 12 **will not** be summarized in tables and will be provided in the listings.

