4.4.3 Analysis of Long Term Efficacy Parameters

Patient overall survival at 60 months

Patients overall survival (OS) status of alive or death, as well as the date of death and date of last known alive will be collected at the Month 60 visit.

OS is defined as: Date of Death or date of last known alive - Date of Surgery + 1

Patients who are still alive will be censored at the 60 month visit date or last known date alive, whichever occurs last. Median OS will be tabulated and Kaplan Meier (K-M) graph will also be included.

HAV interventions

HAV interventions will be listed.

Evidence of aneurysmal dilatation or stenosis of the HAV

Evidence of aneurysmal dilatation or stenosis of the HAV will be listed.

Patency of the HAV (primary, primary assisted, secondary)

Patency of the HAV (primary, primary assisted, secondary patency rates) will be presented for Months 18, 24, 30, 36, 42, 48, 54 and 60. Clopper-Pearson CIs will be presented for frequency counts of patency rates.

Limb salvage/amputation

Limb salvage/amputation at 18, 24, 30, 36, 42, 48, 54 and 60 months will be listed for all subjects who have not died, withdrawn, or been lost to follow-up.

Surgical Revascularization

Incidence of surgical revascularization of the implanted limb, at the level of the HAV or distal to HAV, will be listed for all patients who have not died, withdrawn, or been lost to follow-up.

VascuQol Quality of Life Questionnaire

VascuQol PAD symptom assessment consists of 25 questions. The total score and the 5 domain scores (Activity, Symptom, Pain, Emotional, and Social) will be recorded in the clinical database at 18, 24, 30, 36, 42, 48, 54 and 60 months. VascuQol results will be listed and summarized for all patients who have not died, withdrawn, or been lost to follow-up.

Final Analysis 17/23

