4.4.4 Other Efficacy Variables

High Resolution Ultrasound

Doppler ultrasound (HAV patency) high resolution ultrasound data will be listed.

Time to loss of patency

Time after first implantation of HAV until loss of patency (primary, primary assisted and secondary) will be separately presented in tables using descriptive statistics. The time to loss of patency will be verified during the DRM using all data from the CRF including the information used for patency rates at each visit and information on any AEs and consequent interventions.

Patients discontinued early with the HAV still patent, will be censored at that timepoint.

The median times (or the lower quartile – in case the median is unable to be estimated) will be presented together with the respective 95% CIs using Kaplan-Meier estimates. In case of small numbers of events these analyses may be skipped.

For the 1-year interim analysis, time to loss of patency will be reviewed for the first 12 months, and rates of 3, 6, and 12 months will be presented. For the final analysis, time to loss of patency will be reviewed for the entire study and rates of 3, 6, 12, 24, 36, 48, and 60 months will be presented.

Focused vascular assessment exam will be listed.

Angiography and Endothelium-dependent, flow-mediated vasodilation data will be listed.

5 Safety Analysis

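### To Month 60, the two planned ways of handling death in the patency K-M curves neither give nor bracket the share of implanted patients who lose patency

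*SAP*

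**What the plan says.** SAP 4.4.1 plans K-M curves for primary, primary assisted and secondary patency, which "will be created at the 1-year report and for all subsequent reports". Death, withdrawal and loss to follow-up are handled in two ways:

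- Method (a): "Patients who die, withdraw from the study, or are lost to follow-up are censored at the day of the respective event".
- Method (b): the same patients "are considered as having suffered failure of secondary patency at the day of the respective event". This wording names secondary patency only, although it is given for all three curves.

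SAP 4.4.4 (time to loss of patency) follows the first rule: "Patients discontinued early with the HAV still patent, will be censored at that timepoint". It does not name death separately. For the final analysis, "rates of 3, 6, 12, 24, 36, 48, and 60 months will be presented".

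The visit-wise patency rates in SAP 4.4.3 "will be presented for Months 18, 24, 30, 36, 42, 48, 54 and 60" with Clopper-Pearson intervals, but SAP version 2.0 gives no rule for patients who have died by then. Protocol 9.3 treats anyone who discontinued before the visit as non-patent for any reason, which again merges loss with exit.

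Neither document plans a competing-risk estimate. SAP 4.4.3 does collect death dates and plans a K-M analysis of overall survival.

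**The concern.** A patient who dies with a patent HAV can no longer lose it, so death competes with loss of patency. Method (a) describes loss as it would be if death did not remove anyone. Method (b) describes loss or exit. Neither is the probability that an implanted patient goes on to lose patency. Two curves under opposite rules look like a sensitivity range, and a reader may assume that this probability lies between them. When there are deaths with a patent HAV, it lies below both failure curves.

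What is at stake is how the five-year results are read. Long-term patency is a listed endpoint, an addendum with data to 60 months goes to regulators (Protocol 11), and Protocol 9.3 says the results will inform the sample size of later studies. Someone counting expected patency losses from one minus a planned curve would count too many.

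**Working it through.** **Inputs.** SAP 1.5 gives 15 patients recruited. The documents give no mortality assumption for this trial, so I use the sister PAD study (Protocol 2.4.3): 20 implanted, and "Of the seven patients terminating the study early, three died and four were withdrawn after occlusion of the HAV". Its K-M patency with deaths censored was 84.2% (Month 12) and 73.7% (Month 24) for secondary, and 63.3% and 58.1% for primary. Applying these rates here and extending them beyond Month 24 is my assumption.

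**Reproducing the sister study's figures.** With 19 at risk, that is, 1 of 20 censored before the first loss, the product-limit estimates are 17/19, 16/19, 15/19 and 14/19 = 89.5%, 84.2%, 78.9% and 73.7%. The protocol states 89.5%, 84.2%, 79.0% and 73.7%. At Month 24, 1 − K-M = 26.3%, against 5 losses in 20 patients = 25.0%, a gap of 1.3 points. Counting deaths as failures gives 35% to 40% (7 or 8 of 20).

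**Formulas** (h = yearly loss hazard, m = yearly death hazard, T in years, deaths only):

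- Method (a): 1 − exp(−hT)
- Method (b): 1 − exp(−(h+m)T)
- Share losing patency (cumulative incidence): h/(h+m) × [1 − exp(−(h+m)T)]

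**Hazards.**

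- Death: m = −ln(0.85)/2 = 0.081.
- Constant loss hazard: −ln(0.737)/2 = 0.153 (secondary); −ln(0.581)/2 = 0.272 (primary).
- Two-rate loss hazard (Year 1, then the Months 12–24 rate carried on): −ln(0.842) = 0.172, then −ln(0.737/0.842) = 0.133 (secondary); −ln(0.633) = 0.457, then −ln(0.581/0.633) = 0.086 (primary). The formulas are applied to Year 1 and then to Years 2–5 among those still at risk.

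**Month 60, loss of patency (%).**

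| Case | (a) | (b) | Share | (a) excess, points |
|---|---|---|---|---|
| Secondary, constant | 53.4 | 68.9 | 45.0 | 8.4 |
| Secondary, two-rate | 50.6 | 67.1 | 43.0 | 7.6 |
| Primary, constant | 74.3 | 82.9 | 63.8 | 10.5 |
| Primary, two-rate | 55.1 | 70.1 | 50.0 | 5.1 |

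The constant hazard does not fit primary patency. It implies 23.8% loss at Month 12, but the sister study had 36.7% (100 − 63.3). The two-rate figure, about 5 points, is the one to use.

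**Month 12.** Secondary: 14.2% against 13.6%, an excess of 0.5 point (0.6 with two rates). Primary: 0.9 point (constant) or 1.3 (two-rate).

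**Sensitivity at Month 60 (secondary, constant hazard).**

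- With 0.5 to 1.5 times the death rate, the excess of (a) is 4.5 to 11.9 points.
- With 24-month mortality from 5% to 30%, (a) stays at 53.4%, (b) runs from 59.0% to 80.9%, and the share falls from 50.5% to 37.3%.

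**Scale.** In simulated trials of 15 patients, the standard error of the Month 60 K-M estimate is about 14.5 points for secondary patency (constant hazard) and 14.1 for primary (two-rate). The excess is therefore 8.4/14.5 = 0.58 and 5.1/14.1 = 0.36 of a standard error. In patients, 8.4 points is 0.084 × 15 = 1.3. In 20,000 simulated trials, neither failure curve fell below the cumulative incidence estimate.

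**The case against.** The strongest reply is that nothing here is an error. The endpoints are patency rates and time to loss of patency, not the proportion of patients losing the HAV. The SAP states both rules openly, and (a) is a valid estimate of patency with deaths censored. This stands: (a) overstates only when one minus the curve is read as a share of patients. What remains is that the SAP does not say which quantity it wants and plans no output that clearly gives that share.

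A reader might go further and infer three things that the documents do not support:

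- *Method (a) blurs comparison with series of different mortality.* The reverse holds. In the sensitivity check (a) does not move with mortality, while the cumulative incidence does. The protocol (2.5.3) intends comparison with historical grafts and reports the sister study with deaths censored, so (a) suits that use.
- *Censoring biases graft durability against the HAV.* Cumulative incidence would make the same graft look more durable in a sicker cohort. It is not the better measure of the graft itself.
- *Median times come out too high.* If anything, measured against the share of patients, overstated loss makes the median time to loss too short.

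The other side is also right that the sizes are soft. Three deaths in 20 has an exact 95% interval of about 3% to 38%, the protocol does not say whether those patients had patent HAVs, and SAP 4.4.4 allows its estimates to be skipped if events are few. Nor is the direction unconditional. If 30% of true losses were recorded only as withdrawals, (a) would give 41.4% against a true 45.0%; the two are about equal at 20% (45.7%).

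**Conclusion.** The point holds as a minor improvement. Given at least some deaths with a patent HAV (for (a), before a later loss in another patient) and non-informative withdrawal, the share of implanted patients losing patency lies below both planned failure curves, so (a) and (b) do not bracket it. On sister-study rates carried to Month 60, (a) is high by about 8 points for secondary patency (7.6 to 8.4) and about 5 for primary. The 10.5 points for primary under a constant hazard should not be relied on. Method (b) is further off, and in practice withdrawals and losses to follow-up would add to its excess.

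The Month 12 primary analysis is hardly affected. The study is descriptive with 15 patients and the base-case excess is below one standard error, so no test or decision rule changes. A reader might infer that the K-M analyses are wrong and should be replaced; the documents do not support that. With no deaths among patients with a patent HAV, the excess of (a) is zero.

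**What to change.** Keep K-M methods (a) and (b). For the final analysis, add to SAP 4.4.1 or 4.4.4 an Aalen-Johansen cumulative incidence of loss of primary, primary assisted and secondary patency, with death before that loss as the competing event and 95% confidence intervals at Months 24, 36, 48 and 60. In SAP 4.4.4, label the K-M rates as patency with deaths censored and state that they are not the proportion of patients losing patency.

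The cost is a few sentences in the SAP and one standard estimate per patency type, from loss and death dates that are already collected. The downside is one more curve per patency type to explain.

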1.4 Objectives

1.4.1 Primary Objectives:

This is an open label Phase 2 study. There is no formal hypothesis testing.

Statistical Analysis Plan	
CLN-PRO-004	

Final Analysis 8/23

Safety:

• To evaluate the safety and tolerability of the Humacyte HAV in PAD patients undergoing femoro-popliteal bypass surgery

Efficacy:

- To determine the patency (primary, primary assisted and secondary) rate of the Humacyte HAV at Month 12
- To determine the incidence of hemodynamically significant stenosis (>70%) defined by duplex ultrasound, and the time to stenosis development

1.4.2 Secondary Objectives:

Safety:

- To assess changes in the panel reactive antibodies (PRA) response after HAV implantation
- To determine mechanical stability of the HAV based on freedom from aneurysmal degeneration on duplex ultrasound and computed tomography (CT) imaging
- To determine HAV durability in terms of freedom from need for HAV explanation or replacement due to infection, bleeding or conduit degeneration

Efficacy:

- To determine the patency of the HAV (primary, primary assisted and secondary) at Months 3, 6 and 9
- To determine the rates of interventions needed to maintain / restore patency in the HAV through Month 12
- To assess effect of HAV implantation on symptoms of PAD using the VascuQol instrument
- To assess effect of the HAV on ankle-brachial index (ABI)
- To assess effect of the HAV on 6 minute walk test

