1.5 Sample Size Estimation

Up to 25 patients were planned, and 15 patients were recruited into the study. As this Phase 2 study is one of the first studies of the HAV in humans with PAD, the number of patients was chosen in order to provide preliminary evidence of safety and efficacy of the HAV to allow the initiation of further trials in larger numbers of patients.

The study is not powered to assess the efficacy of the HAV.

2 Efficacy and Safety Variables

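### Time to first stenosis, part of a primary efficacy objective, is summarised only in patients who had a stenosis, with no censored or cumulative-incidence estimate planned

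*SAP*

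**What the plan says.** SAP section 1.4.1 lists as a primary efficacy objective "To determine the incidence of hemodynamically significant stenosis (>70%) defined by duplex ultrasound, and the time to stenosis development". Protocol section 3.1 has the same objective.

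SAP section 4.4.1 (Efficacy Objective #2) plans two stenosis outputs:

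- **Counts by planned visit up to Month 12.** Events between visits are assigned to the next planned visit. In the SAP's example for Day 29, the table "will denote the number of patients with stenosis events that occurred after Day 5, and up to Day 29 (inclusive of Day 29". These are therefore counts per interval.
- **Time of first stenosis**, calculated as the "number of days from HAV implantation to date of first stenosis event". For this summary, "Patients who did not have a stenosis event will not contribute a value for this summary".

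Other time-to-event outcomes use all implanted patients. SAP 4.4.1 plans Kaplan-Meier curves for patency under two rules for death, withdrawal and loss to follow-up. SAP 4.4.4 says of time to loss of patency: "Patients discontinued early with the HAV still patent, will be censored at that timepoint". SAP 4.4.3 says of overall survival: "Patients who are still alive will be censored at the 60 month visit date or last known date alive, whichever occurs last". The only other rule on time to first stenosis is the partial-date imputation in SAP 7.2.

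**The concern.** A mean or median taken only over patients with an event answers this question: given a stenosis within follow-up, when was it found? The objective asks how long implanted patients go before a stenosis develops. The two answers can differ widely when most patients have no event, because the event-only figure is bounded by the follow-up window and takes no account of how many patients stayed free of stenosis.

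Early exits also need a rule. In the earlier PAD study (Protocol 2.4.3, 20 patients, 24 months), "Of the seven patients terminating the study early, three died and four were withdrawn after occlusion of the HAV". Death or final loss of the HAV rules out a later stenosis and is not ordinary censoring.

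At stake is how the result reads. Protocol 2.5.3 says the data will be compared with historical data on synthetic grafts, and Protocol 9.3 says the results will be used to size later studies. A typical time to stenosis of about half a year could be taken as a property of the graft when it mostly reflects a one-year window.

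**Working it through.** The plan gives no expected incidence or time of stenosis, so there is no figure of its own to reproduce. The calculations below are illustrations.

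**Inputs.** Sample size is from SAP 1.5: "Up to 25 patients were planned, and 15 patients were recruited into the study". The tabulation window is 12 months (SAP 4.4.1), taken as 365 days. Incidences, the constant hazard and the exit pattern are assumptions.

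**Step 1: does the event-only summary respond to risk?** Let p be the 12-month incidence, with full follow-up and hazard L = -ln(1 - p)/365.

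- Event-only median = -ln(1 - p/2)/L
- Mean stenosis-free time within 365 days, all patients = p/L
- Chance of no stenosis among 15 patients = (1 - p)^15

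| p | L per day | Event-only median (days) | Mean stenosis-free time to day 365 (days) | Chance of no event |
|---|---|---|---|---|
| 10% | 0.000289 | 0.0513/L = 177.7 | 346.4 | 20.6% |
| 30% | 0.000977 | 0.1625/L = 166.3 | 307.0 | 0.5% |
| 50% | 0.001899 | 0.2877/L = 151.5 | 263.3 | <0.1% |

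From p = 10% to 50% the event-only median falls by 177.7 - 151.5 = 26 days. The all-patient mean falls by 346.4 - 263.3 = 83 days, and the cumulative incidence itself goes from 10% to 50%. At 10% incidence the event-only summary rests on 15 × 0.10 = 1.5 patients on average, and about one time in five it would be empty.

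**Step 2: how much do early exits matter?** Assume 15 patients, stenoses at days 90, 180 and 270, four event-free patients leaving at day 150, and eight event-free at day 365. The Aalen-Johansen estimate adds, at each stenosis, the probability of being event-free just before it, divided by the number at risk (15, 10 and 9).

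- All four exits are competing events: 1/15 + (10/15)/10 + (9/15)/9 = 20.0%
- Two competing, two censored: 1/15 + (12/15)/10 + 0.72/9 = 22.7%
- All four censored: 1/15 + (14/15)/10 + 0.84/9 = 25.3%, which equals 1 minus Kaplan-Meier

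The 95% intervals (delta-method variance, log(-log) scale) are 4.9% to 42.4%, 5.4% to 46.9% and 5.9% to 51.5%. The crude proportion is 3/15 = 20% in every case. The event-only mean and median are 180 days in every case.

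**Step 3: which exits really end the time at risk?** SAP 4.4.1 lets secondary patency continue through procedures that reopen the HAV, and Protocol 2.4.3 reports that most interventions in the earlier study did restore patency. An occlusion that is reopened therefore leaves the patient at risk of stenosis. Stenosis and thrombosis can also be found together: Protocol 8.2 describes stenoses found alongside a thrombosis, and SAP 4.4.1 lists an intervention type for stenosis with thrombosis.

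**The case against.** **The study is small and descriptive.** It has no hypothesis test, no efficacy power and 15 patients, and SAP section 4 calls all results exploratory. This stands, and it limits the severity. But estimates are all that a descriptive study produces, and the SAP already plans Kaplan-Meier for patency in the same 15 patients.

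**The by-visit counts suffice.** Together with the number of patients per visit (SAP 4.1), they show crude incidence and roughly when stenoses appear. A stenosis that leads to intervention also ends primary patency, which has Kaplan-Meier curves. A reader might infer that this part of the objective has no usable output at all; the documents do not support that. What remains is that the counts carry no stated rule for patients who have left, and the one summary labelled as time to first stenosis leaves out event-free patients.

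**Early exits change little.** This also stands. A reader might infer that the crude count seriously misstates 12-month incidence. In Step 2 it matches the competing-risk estimate exactly when all exits are deaths or HAV loss, and otherwise differs by at most 5.3 percentage points, against intervals spanning nearly 40 points or more. The exits in the earlier study occurred over 24 months in other patients, so they show that a rule is needed and not how often it will apply.

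**Onset is not observed.** Duplex is scheduled at Day 29 and Months 3, 6, 9 and 12, so any estimate from these data is of time to detection. This is correct and belongs in the labelling.

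**Conclusion.** The concern holds as an analysis gap that should be fixed. The planned time summary is conditional on having a stenosis and does not estimate time to stenosis in implanted patients, although time to stenosis is part of a primary objective and the SAP uses censored methods for patency and survival.

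On size: a fivefold rise in 12-month incidence moves the event-only median by only 26 days. This rests on an assumed constant hazard and complete follow-up. The effect of early exits, under an assumed pattern of four exits at day 150, is small next to the sampling uncertainty, so the main defect is the quantity being summarised. No test, error rate or decision rule is affected.

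A reader might also infer that every HAV occlusion should count as a competing event. The documents do not support that: patency can be restored after occlusion, and ending follow-up at the first occlusion could miss later stenoses or those found with the thrombosis.

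**What to change.** In SAP 4.4.1, Efficacy Objective #2, replace the event-only summary with an Aalen-Johansen cumulative-incidence estimate of first detected >70% stenosis in all implanted patients from Day 1, with 95% confidence intervals at Months 3, 6, 9 and 12. Keep the by-visit counts and move the event-only times to a listing. Specify that:

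- the event is the first scheduled or unscheduled duplex showing >70% stenosis, and a >70% stenosis documented at a thrombosis or its treatment also counts;
- competing events are only death, HAV removal and final abandonment (including an occlusion never reopened) before a stenosis;
- an occluded HAV whose patency is restored stays at risk;
- other event-free patients are censored at their last duplex without >70% stenosis;
- the Month 12 estimate includes the +14-day visit window, so that stenoses found at an on-window visit after day 365 are not lost;
- the result is labelled time to detection.

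Report 1 minus Kaplan-Meier as a sensitivity analysis.

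The cost is SAP wording and one more table, from data largely already collected. One check is needed first: that the database holds a dated >70% result for each duplex, since the stenosis source that SAP 4.4.1 names for deriving patency is adverse event terms with no percentage. The downside is wide intervals with 15 patients.
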